7.2 Visit procedure

All subjects who don't withdraw from this study, will be followed up for 2 years.

7.2.1 Screening/Baseline

At the initial study visit, the subject will be informed of the study objectives and overall requirements, and written informed consent will be obtained prior to any study specific assessments. The subject will then undergo a brief clinical evaluation to ensure compliance with the inclusion and exclusion criteria to determine the eligibility (see Section 5.2).

Data for all subjects will come from the subjects' Screening or Baseline Visits and the subjects' medical records:

The following must be completed before Gn Initiation:

- Visit date
- Subject Name and hospital subject number will be recorded and kept confidentially in the clinic solely for the purposes of generating a unique study subject number which will be used to anonymously identify each subject in the study.
- Demographic details including age, gender, date of birth and ethnic origin
- Weight and height
- Clinical and gynecological examination
- Gynecological history: duration of infertility, menstrual cycle, History of miscarriages, history of pelvic surgery; history of ovarian surgery.
- Medical history and concomitant illness
- Any concomitant medication taken by the subject when entering the study
- Concomitant medications prescribed and reasons
- Ability to conceive and times of IVF attempts
- In vitro fertilization-embryo transfer and ICSI indications assessment
- The following data should be collected (data within 3 months before Screening is accepted)
 - FSH and estrogen (E2) levels during the early follicular phase (Cycle Day 2 to 4)
 - AFC (follicles ≥ 2 mm and < 11 mm) assessed in the early follicular phase (Cycle Day 2 to 4)

After randomization, blood samples for AMH test should be collected in each site, and the analysis will be performed in central lab. The analysis result of AMH test will be used in final statistical analysis, not for guiding the clinical medication.

7.2.2 Gn Initiation

After randomization, the subjects will receive either long GnRH-a protocol or GnRH- ant protocol for COS in supposed normal ovarian responders, the procedures are described as follows:

1: GnRH agonist long protocol

GnRH-a will be administered for about 14 to 20 days until down-regulation is satisfied as judged by Investigator. Satisfied down regulation criteria can be defined as: LH \leq 5 IU, E2 \leq 50 pg/ml, and **endometrium thickness \leq 6mm**. r-FSH (Gonal-f[®]) will be initiated and regimen will be as routinely practiced by Investigators and according to licensed summary of product characteristics (China) label.

The following data will be collected:

- Date of initiation of GnRH-a
- Initial Dose of GnRH-a
- Details of dose adjustments of GnRH-a if any
- LH and E2 levels before Gonal-f[®] initiation
- Date of initiation of Gonal-f[®]
- Initial dose of Gonal-f[®]
- Recording of AEs
- Concomitant medications prescribed and reasons.

2: GnRH antagonist protocol

r-FSH (Gonal-f[®]) will be initiated and regimen will be as routinely practiced by Investigators and according to licensed SmPC label.

The following data will be collected:

- LH and E2 levels before Gonal-f[®] initiation (if measured)
- Date of initiation of Gonal-f[®]
- Initial dose of Gonal-f[®]
- Recording of AEs
- Concomitant medications prescribed and reasons.
-

7.2.3 Triggering Day

1: GnRH agonist long protocol

Follicular development will be monitored according to the Investigator site's ART practice until the criteria to administer r-hCG (Ovidrel[®]) are met to induce final oocyte maturation. r-hCG administration is to be performed according to the site's routine clinical practice.

The following data will be collected:

CELEBRATE Study

MS700623_0020

- No. and sizes of follicles, E2 level and LH level on the day of hCG administration
- Details of dose adjustments of GnRH-a if any
- Treatment days of GnRH-a
- Details of dose adjustments of Gonal-f[®] new pen/ powder injection (75IU) (Sequence and timing of dose adjustment)
- Daily dose and total dose of Gonal-f[®]
- Total number of Gonal-f[®] stimulation treatment days
- Date and dose of hCG administered / other methods performed.

or

- Reason for not administering hCG / take other action such as no optical follicle development, elevated levels of E2 or Progesterone or subject's decision etc.
- If r-LH supplementation is required, as per clinical judgment of the Investigator, indicate the initial dose and date of initiation
- Dose adjustment of r-LH and total dose
- Total number of r-LH treatment days
- Recording of AEs
- Concomitant medications prescribed and reasons.

2: GnRH antagonist protocol

The GnRH-ant will be initiated in a fixed protocol on stimulation days 5 to 6 as per the Investigator site's ART protocol. Follicular development will be monitored according to the Investigator site's ART practice until the criteria to administer hCG are met to induce final oocyte maturation. hCG administration is to be performed according to the site's routine clinical practice.

The following data will be collected:

- No. and sizes of follicles, E2 level and LH level on the day of hCG/GnRH-a administration
- LH and E2 levels prior to GnRH-ant administration and on the day of GnRH-ant initiation if measured
- Date of initiation of GnRH-ant
- Initial Dose of GnRH-ant
- Total dose of GnRH-ant
- Total treatment days of GnRH-ant
- Dose adjustment of GnRH-ant
- Details of dose adjustments of Gonal-f[®] new pen/ powder injection (75 IU) (Sequence and timing of dose adjustment)
- Daily dose and total dose of Gonal-f[®]

- Total number of Gonal-f® stimulation treatment days
- Date and dose of hCG administered
or
- Reason for not administering hCG such as no optical follicle development, elevated levels of E2 or Progesterone or subject's decision etc.
- If r-LH supplementation is required, as per clinical judgment of the Investigator, indicate the initial dose and date of initiation
- Dose adjustment of r-LH and total dose
- Total number of r-LH treatment days
- Recording of AEs
- Concomitant medications prescribed and reasons

7.2.4 Oocytes pick up

The cycle will be canceled if there is no oocyte gained in this visit or the oocytes pick up procedure is not performed, the patient will withdraw from this study and all procedures related to End of Study Visit should be performed..

Oocyte pick up will be performed according to the site's routine practice.

The following data will be collected:

- Date of oocyte pick up
- No. of oocytes retrieved
- No. of metaphase II (MII) oocytes retrieved
- Recording of AEs
- Concomitant medications prescribed and reasons.

7.2.5 Embryo Transfer in fresh cycle

IVF/ICSI, ET and luteal phase support will be performed according to the site's routine practice. Luteal phase support will be started after oocytes retrieval.

The following data will be collected:

- Date of oocyte insemination
- Number of oocytes inseminated
- Endometrial assessment
- Embryo quality
- Methods of insemination
- Number of oocytes fertilized

- Total number of good quality embryos
- Total number of embryos
- Date of embryo transfer
- No. of embryos transferred
- No. of embryos cryopreserved
- Recording of AEs
- Concomitant medications prescribed and reasons.

If the procedure of insemination is not conducted due to any reason, reasons should be specified and all procedures related to End of Study Visit should be performed.

If the procedure of ET in fresh cycle is not conducted and there are no embryos preserved for frozen embryo transfer (FET), reasons should be specified and all procedures related to End of Study Visit should be performed.

If the procedure of ET in fresh cycle is not conducted but there are embryos preserved for FET, further FET visit should be performed.

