Trial centers/countries	This study will be conducted in approximately 5 centers in China
Planned trial period (first subject in-last subject out)	About 34 months
Trial Registry	Register study information on ClinicalTrials.gov

Objectives:
 
Primary objectives
 
 • To investigate the cumulative live birth rates in infertile women ≤ 38 years old with normal ovarian reserve using GnRH antagonist or agonist protocol for COS in ART treatment 
Secondary Objectives
 
 • To investigate the safety and pregnancy outcomes of GnRH antagonist and agonist protocols after the fresh embryo transfer 	

Methodology:
 
This is a Phase IV, prospective, randomized controlled study to investigate the cumulative live birth rates (CLBRs) of gonadotrophin-releasing hormone (GnRH) antagonist protocol (GnRH-ant group) compared with the standard GnRH agonist long protocol (GnRH-a group) for controlled ovarian stimulation in supposed normal ovarian responders.
	

CELEBRATE Study

MS700623_0020

In this study, patients who are planning to undergo IVF/ICSI cycle aged ≤ 38 years old with normal ovarian reserve will be considered for enrollment. Approximately 888 patients will be enrolled at approximately 5 centers in China over a period of 10 months.

About 12-20 visits will be performed in this study for each patient.

The CLBR with first live birth resulting from one initiated COS cycle will be compared between GnRH-a group and GnRH-ant group.

Planned number of subjects: 888

Primary endpoints:

CLBR with first live birth resulting from one initiated COS cycle

Secondary endpoints:

- Number of oocytes retrieved
- Good-quality embryo rate (The Istanbul Consensus²⁹)
- hCG positive rate
- Implantation rate
- Clinical pregnancy rate
- Ongoing pregnancy rate
- Live birth rate
- Cumulative clinical pregnancy rate
- Miscarriage rate
- Ectopic pregnancy rate
- Cycle cancelled rate and reason
- Rate and severity of OHSS
- Time to pregnancy
- Time to live birth

Pharmacokinetics: Not applicable

Other assessments:

To explore the relationship between the number of oocytes retrieved and number of embryos or times of embryo transfer or CLBR

Diagnosis and key inclusion and exclusion criteria:

Diagnosis: Infertile women planning to undergo IVF/ICSI cycle aged ≤ 38 years old with normal ovarian reserve

Inclusion criteria:

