7.3.2 Secondary endpoints

COS and Pregnant outcomes, including:

- Number of oocytes retrieved
- Good-quality embryo rate(The Istanbul Consensus1)
- hCG positive rate
- Implantation rate
- Clinical pregnancy rate
- Ongoing pregnancy rate
- Live birth rate
- Cumulative clinical pregnancy rate
- Miscarriage rate
- Ectopic pregnancy rate
- Cycle cancelled rate and reason
- Rate and severity of OHSS
- Time to pregnancy
- Time to live birth

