8.1 Sample Size

For this non-inferiority trial, a sufficient number of subjects will be enrolled to have at least 80% power to demonstrate the non-inferiority of GnRH antagonist protocol vs GnRH agonist protocol regarding the CLBR using a two-sided 95% confidence interval. The CLBR is expected to be 60% in both groups, and the non-inferiority margin is -10% (absolute). Based on these assumptions, a

sample size of 377 evaluable subjects per arm would provide 80% power to demonstrate the non-inferiority of GnRH antagonist protocol vs GnRH agonist protocol regarding the CLBR. As a result, totally about 888 subjects will be randomized, that is 444 for each treatment group after considering 15% dropout rate.

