8.3.2 Secondary Endpoints

COS and pregnant outcomes, including:

- Number of oocytes retrieved
- Good-quality embryo rate(The Istanbul Consensus1)
- hCG positive rate (in fresh cycle)
- Implantation rate (in fresh cycle)
- Clinical pregnancy rate (in fresh cycle)
- Ongoing pregnancy rate(in fresh cycle)
- Live birth rate(in fresh cycle)
- Cumulative clinical pregnancy rate
- Miscarriage rate(in fresh cycle)
- Ectopic pregnancy rate(in fresh cycle)
- Cycle cancelled rate and reason(in fresh cycle)
- Rate and severity of OHSS(in fresh cycle)
- Time to pregnancy
- Time to live birth

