8.5.3 Analysis of Secondary Endpoints

Definition of some important secondary endpoints:

Clinical pregnancy: a pregnancy diagnosed by ultra-sonographic visualization of one or more gestational sacs or definitive clinical signs of pregnancy. It includes ectopic pregnancy. Note: Multiple gestational sacs are counted as one clinical pregnancy.

Clinical pregnancy rate: the number of clinical pregnancies expressed per 100 initiated cycles, aspiration cycles, or embryo transfer cycles. Note: When clinical pregnancy rates are given, the denominator (initiated, aspirated, or embryo transfer cycles) must be specified.

Cumulative clinical pregnancy rate: Numerator is the No. of women got their first clinical pregnancy, the Denominator is the No. of women who attempt the ovarian stimulation.

Live birth rate: Numerator is the No. of women got live birth resulting from fresh cycle (multiple births considered as one live birth), the Denominator is the No. of women who attempt the ovarian stimulation.

Implantation rate: the number of gestational sacs observed divided by the number of embryos transferred.

Ongoing pregnancy: intrauterine pregnancy continued for 12 gestational weeks (detection of presence of gestational sac with fetal heartbeat by transvaginal ultrasound examination in week 12).

Time to pregnancy: time from Gn Initiation to the first clinical pregnancy.

Time to live birth: time from Gn Initiation to the first live birth.

Cancelled cycle: an ART cycle in which ovarian stimulation or monitoring has been carried out with the intention to treat, but which did not proceed to follicular aspiration or, in the case of a thawed embryo, to embryo transfer.

Miscarriage, also known as spontaneous abortion and pregnancy loss, is the natural death of an embryo or fetus before it is able to survive independently

The analysis of the secondary endpoints are intended to provide additional characterization of the treatment effect.

Number, time, percentages and related CIs will also be reported for the following secondary endpoints:

- Number of oocytes retrieved
- Good-quality embryo rate(The Istanbul Consensus1)
- hCG positive rate (in fresh cycle)
- Implantation rate (in fresh cycle)
- Clinical pregnancy rate (in fresh cycle)
- Ongoing pregnancy rate(in fresh cycle)
- Live birth rate(in fresh cycle)
- Cumulative clinical pregnancy rate
- Miscarriage rate(in fresh cycle)
- Ectopic pregnancy rate(in fresh cycle)
- Cycle cancelled rate and reason(in fresh cycle)

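### Fresh-cycle pregnancy endpoints, including miscarriage and ectopic pregnancy, depend on how often each arm freezes all embryos, yet the plan records no reason for freezing all and reports no freeze-all rate

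*Combined protocol and SAP*

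**What the plan says.** **Scope of the endpoints.** The secondary objective in the synopsis is "To investigate the safety and pregnancy outcomes of GnRH antagonist and agonist protocols after the fresh embryo transfer". Sections 8.3.2 and 8.5.3 restrict hCG-positive, implantation, clinical pregnancy, ongoing pregnancy, live birth, miscarriage and ectopic rates to the fresh cycle. The synopsis list and 7.3.2 carry no such limit: 7.3.2 has only "Miscarriage rate", where 8.3.2 has "Miscarriage rate(in fresh cycle").

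**What is recorded when no transfer takes place.** Section 7.2.5 asks for a reason if insemination is not done, and if there is no fresh transfer and nothing is frozen. Section 7.2.6 asks for one if a frozen transfer is not done. For freeze-all, 7.2.5 says only: "If the procedure of ET in fresh cycle is not conducted but there are embryos preserved for FET, further FET visit should be performed".

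**Cancellation.** Under 8.5.3 a cycle is cancelled if it does not reach aspiration or, for a thawed embryo, does not reach transfer. Freezing all embryos after retrieval is neither. Section 7.2.11 uses cycle cancellation for terminated treatment, with OHSS and risk of OHSS among the reasons.

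**Denominators.** Section 8.5.3 fixes the fresh live birth rate and the cumulative clinical pregnancy rate per woman starting stimulation, and the implantation rate per embryo transferred. For clinical pregnancy it offers three options and adds: "When clinical pregnancy rates are given, the denominator (initiated, aspirated, or embryo transfer cycles) must be specified". It selects none. Hormonal, ongoing pregnancy, miscarriage and ectopic rates have no stated denominator. The synopsis, however, says that secondary rates follow the methods of the conservative CLBR, and 8.5.1 treats a subject without evidence of pregnancy as a failure.

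**The concern.** Whether a fresh transfer takes place is decided after randomisation, in an open-label trial (5.4), under each site's routine practice (7.2.5). Section 3 cites earlier work in which the two protocols differed in oocyte yield and OHSS incidence, so the freeze-all share may differ by arm. The documents do not say by how much or in which direction.

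If it does differ, a per-woman fresh-cycle rate is lower in the arm that freezes more, even when each transfer does equally well. A per-transfer rate compares two subsets selected after randomisation. A reader of the results would need the freeze-all rate and its reasons by arm to tell a poorer transfer outcome from a deferred transfer, and the plan promises neither.

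For miscarriage and ectopic pregnancy the distortion flatters. Fewer fresh transfers mean fewer fresh pregnancies that can be lost or be ectopic. The events that follow the later frozen transfers are left out of these two endpoints, although the pregnancies concerned contribute to the CLBR.

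**Working it through.** **1. The plan's own figure.** Section 8.1 assumes "The CLBR is expected to be 60% in both groups, and the non-inferiority margin is -10% (absolute"), with 80% power and a two-sided 95% interval. n per arm = (1.960 + 0.842)² × (0.60 × 0.40 + 0.60 × 0.40) / 0.10² = 377. With 15% dropout, 377 / 0.85 = 443.5, so 444 per arm and 888 in total. This reproduces exactly and does not change. It serves below only as the trial size.

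**2. Is the reason recoverable?** Section 5.1 asks for a reason when a woman discontinues the treatment cycle. Section 7.2.11 collects the reason for completing observation. A freeze-all woman does neither, because 7.2.5 sends her on to FET. The date of fresh transfer, embryos transferred, embryos cryopreserved (7.2.5), and fresh transfer and FET yes/no (7.2.12) are collected. The share by arm can therefore be derived; the reason cannot be obtained from the listed fields.

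**3. Size of the shift in fresh live birth.** The documents give no freeze-all or per-transfer rates, so these inputs are assumptions: the same live birth rate p per fresh transfer in both arms; 10% of women without fresh transfer for other reasons; freeze-all of 20% in the agonist arm; n = 444 per arm.

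Per-woman rate = p × (1 − 0.10 − freeze-all share), so the difference between arms = p × (gap in freeze-all).

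At p = 45% the agonist rate is 0.45 × 0.70 = 31.5%.

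| Antagonist freeze-all | Antagonist per-woman rate | Difference (points) | 95% CI half-width (points) | Chance of two-sided p < 0.05 |
|---|---|---|---|---|
| 20% | 31.5% | 0 | 6.1 | 5% |
| 30% | 0.45 × 0.60 = 27.0% | −4.5 | 6.0 | 31% |
| 35% | 0.45 × 0.55 = 24.75% | −6.75 | 5.9 | 61% |
| 40% | 0.45 × 0.50 = 22.5% | −9.0 | 5.8 | 86% |

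For a 10 to 20 point gap, the shift is 3.5 to 7.0 points at p = 35% and 5.5 to 11.0 points at p = 55%. If the agonist arm freezes more (30% against 20%, p = 45%), the difference is +4.5 points. The per-transfer difference is zero throughout, by construction.

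**4. The two scales can point in opposite directions.** Assume 45% against 50% per transfer and fresh transfer in 70% against 55% of women. The second arm is better by 5 points per transfer. Per woman it is worse: 0.45 × 0.70 = 31.5% against 0.50 × 0.55 = 27.5%. The same arithmetic applies to the fresh clinical pregnancy rate, for which 8.5.3 leaves both scales available.

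**5. Miscarriage and ectopic pregnancy.** Let m be the risk of the event per fresh transfer, equal in both arms. The fresh-only per-woman rates are m × 0.70 and m × 0.60, 0.55 or 0.50. Their ratios are 0.86, 0.79 and 0.71, so the arm with more freeze-all shows 14%, 21% or 29% fewer events whatever the value of m. Section 8.5.3 also counts an ectopic pregnancy as a clinical pregnancy. A first clinical pregnancy that is ectopic after FET therefore counts as a success in the cumulative clinical pregnancy rate and never as an event in the ectopic rate.

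**The case against.** The strongest reply is that a per-woman fresh-cycle rate is a valid randomised comparison whatever the reason for deferral. Section 6.1 says that the trial compares protocols, so freezing caused by a protocol is part of that protocol's effect. The fresh live birth denominator is fixed, and the synopsis together with 8.5.1 points to the same per-woman basis for the other pregnancy rates. Some likely drivers of deferral are recorded in any case: OHSS, endometrial assessment and trigger-day estradiol. The endpoints are described as supportive, and the primary CLBR counts fresh and frozen transfers alike. Women with PCOS or an AFC above 20 are excluded. The eCRF and the operations manual are not among the documents, so a reason field may exist there.

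Most of this stands, and it limits the point. A reader might infer that arm differences in fresh outcomes cannot be separated from freeze-all at all, that every denominator is open, or that pregnancies after FET enter no secondary analysis. The documents support none of these. The freeze-all share and per-transfer rates can be derived, three secondary rates have fixed denominators, and a first clinical pregnancy after FET enters the cumulative clinical pregnancy rate and time to pregnancy.

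Three things remain. Validity of the per-woman comparison does not tell the reader whether a difference reflects deferral, or why transfer was deferred. The protocol requires a reason in the other no-transfer branches of 7.2.5 and in 7.2.6, but not in this one. The protocol-effect argument also does not justify leaving out miscarriages and ectopic pregnancies after FET, which belong to the same randomised protocol.

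**Conclusion.** The point holds for the secondary fresh-cycle endpoints only; the primary CLBR and the sample size are untouched. The plan ties seven pregnancy outcomes to an event that may differ by arm, asks for no reason in the freeze-all branch, leaves these women outside the cancelled-cycle rate of 8.5.3, and plans no freeze-all summary. Miscarriage and ectopic pregnancy are the more serious part, because a fresh-only rule can make the arm with more freezing look safer.

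The size is illustrative. With 45% live birth per transfer in both arms, a 10 to 20 point freeze-all gap alone moves the per-woman fresh live birth rate by 4.5 to 9 points, and by 3.5 to 11 points over 35% to 55% per transfer. With no gap there is no shift. The direction depends on which arm freezes more, and the documents do not establish that.

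The open clinical pregnancy denominator is missing detail rather than an error, since the synopsis implies a per-woman basis.

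**What to change.** 1. **Section 7.2.5:** record the reason for every fresh transfer not done, including when embryos are frozen. Report the freeze-all rate and its reasons by randomised arm. The field has to be collected prospectively.
2. **Sections 8.3.2 and 8.5.3:** report miscarriage and ectopic pregnancy by randomised arm over all transfers from the study stimulation, per woman starting stimulation and also per clinical pregnancy. Keep the fresh-only rates as descriptive. Ectopic status (7.2.8) and spontaneous abortion (7.2.10) are already collected, and the synopsis schedule note applies these assessments after every transfer. The 12-week call in 7.2.9, which lists early miscarriage, is for the fresh cycle only, so miscarriages after FET would come from the live birth assessment.
3. **Section 8.5.3:** state that fresh-cycle hCG-positive, clinical and ongoing pregnancy rates use women who start stimulation, as the synopsis implies, with per-transfer rates as description only.
4. **Consistency:** reconcile the cancellation wording of 7.2.11 and 8.5.3, and align the endpoint lists in the synopsis, 7.3.2 and 8.3.2.

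The cost is one eCRF field, a few extra tables and some text. No visits are added and the sample size stays at 888. The one drawback is that per-woman fresh rates will be lower than per-transfer rates; showing both deals with that.
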